**2024**

# **Comparative Study of Clinical Outcomes and Safety between Colistin and Tigecycline for Multi-Drug Resistant Gram Negative Bacteria.**

## **I. Introduction:**

The Centers for Disease Control and Prevention (CDC) and the European Center for Disease Prevention and Control have defined Multi-drug resistant (MDR) Gram-negative bacteria as acquired non-susceptibility to at least one drug in three or more antimicrobial categories. Extensively drug-resistant (XDR) Gram-negative bacteria was defined as non-susceptibility to at least one agent in all but two or fewer antimicrobial categories (i.e. bacterial isolates remain susceptible to only one or two categories). Pan drug-resistant (PDR) was defined as non-susceptibility to all agents in all antimicrobial categories (1).

MDR, XDR and PDR of *Escherichia coli*, *Klebsiella pneumoniae*, *Enterobacter* spp., *Acinetobacterbaumannii*, and *Pseudomonas aeruginosa* have been known by difficult-to-treat (DTT) infections that not respond to treat with as  $\beta$ -lactams, including carbapenems, extended-spectrum cephalosporins such as ceftazidime, ceftriaxone, and cefepime and  $\beta$ -lactam/  $\beta$ -lactamase inhibitor combinations, and fluoroquinolones(2).

In the past few decades, bacteria developed various mechanisms of resistance to almost available antibiotics as tetracycline, beta-lactams, fluoroquinolones and aminoglycosides. Colistin and tigecycline have become the last treatment for MDR gram negative bacteria(3)(2).

Colisin is polymyxin E antibiotic. Colistin has a unique mechanism of action against MDR and XDR bacteria regardless of the resistance. Colistin has an antimicrobial activity against aerobic Gram-negative bacteria(4). Colistin is the last choice treatment for life-threatening infections, such as carbapenem-resistant *P. aeruginosa*, *E. coli*, *A. baumannii*, *K. pneumoniae*, and other *Enterobacteriaceae*(3).

Although, colistin has a good antimicrobial activity against MDR and XDR, some old literatures reported that colistin associated with high side effects as neuorotoxicity, neuromuscular blockade, hematotoxicity and nephrotoxicity and mortality risk (5)(6). In 1970, the use of colistin was limited for treatment patients with cystic fibrosis only. Latterly, some new studies reported that colistin's side

effects are less common than old studies and they resolved after discontinuation of colistin in severe cases (7).

Tigecycline belongs to a tetracycline class that used for the treatment of MDR infections (gram negative and gram positive bacteria). In 2005, the Food and Drugs Administration (FDA) approved tigecycline that administrated in a parenteral form. The FDA reported in 2010 that the treatment with tigecycline was associated with high risk for mortality (8). Recently, tigecycline has been used for treatment complicated intra-abdominal infections (CIAI), complicated skin and skin structures infections (CSSTI) with the exclusion of diabetes foot infection, and community-acquired bacterial pneumonia (CAP) as monotherapy in adult(9).

The FARES and the clinical trial studies suggested that tigecycline administration associated with gastrointestinal symptoms (nausea, vomiting and diarrhea), pancreatitis, increased hepatic function, jaundice, cholestatic, bleeding risk, thrombocytopenia and Steven-Johnson syndrome(8)(10).

The objective of this study to prospectively compare between the clinical outcomes and safety of colistin and tigecycline in patients with MDR gram negative bacteria in Intensive Care Unit.

## **II. Aim and objectives:**

Objective from this study to compare the clinical outcomes and safety between colistin and tigecycline for multi-drug resistant gram negative bacteria.

## **III. Method and material:**

### **Study site:**

Study will be in Beni-Suef university hospital.

### **Study design:**

Prospective randomized controlled study. The method of randomization was a sealed envelope technique.

### **Study duration:**

The study will be conducted from December 2024 to May 2025.

### **Study population:**

- **Group I:** 66 patients received intravenous **colistin** 300 mg colistin base activity (CBA) as **loading dose, followed by** 2.5–5mg/kg/day of CBA in 2 divided doses as **a maintenance dose** in intensive care unit to treat their MDR infection.(11)
- **Group II:** 66 patients received intravenous **tigecycline** 100 mg single dose as **loading dose**, followed by 25-50 mg every 12 hours **maintenance dose** in intensive care unit to treat their MDR infection(12).

### **Sample size technique:**

Sample size was calculated using G\*Power (3.1.9.4) software for windows using Fisher analysis test. A total sample size of 132 participants was estimated for 95% power,  $\alpha$ - error probability 0.05. Analysis of data was performed using IBM SPSS v. 25 (Statistical Package for Social science) for Windows.

### **Sample size calculation:**

**Exact - Proportions:** Inequality, two independent groups (Fisher's exact test)

**Options:** Exact distribution

**Analysis:** A priori: Compute required sample size

Input:	Tail(s)	= Two
	Proportion p1	= 0.58
	Proportion p2	= 0.261
	$\alpha$ err prob	= 0.05
	Power (1- $\beta$ err prob)	= 0.95
	Allocation ratio N2/N1	= 1
Output:	Sample size group 1	= 66
	Sample size group 2	= 66
	Total sample size	= 132
	Actual power	= 0.9501125
	Actual $\alpha$	= 0.0316077

### **Inclusion criteria:**

Study will include adult patient (male, female), (age from 18 to 70 years) admitted to intensive care unit in study period (six months) who received intravenous colistin or tigecycline as antimicrobial drug for treatment their MDR gram negative infection (13).

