### **Exclusion criteria:**

- Patient admitted to intensive care unit younger than 18 years or older than 70 years (14).
- Liver transplantation patients.
- Patients are chronic kidney disease (CKD on hemodialysis or baseline creatinine clearance (crcl) < 10 ml/min (estimated by Cockcroft Gault equation).
- Patients received renal replacement therapy before or during admission.
- Patient is on any other nephrotoxic drug (vancomycin, aminoglycosides, NSAIDs, cyclosporine, amphotericin B, etc.) (Aggarwal & Dewan, 2018).
- Pregnant and lactating women (16).
- Patients refused the consent of the study.

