### **Study procedure:**

- Demographic and medical history for all patients included in this study will be recorded.
- Complete physical examination for all patients included in this study will be taken.
- Basic routine investigation for all patients included in this study will be measured as Complete blood Count test (CBC), blood pressure and temperature.
- Improvement of signs and symptoms after the end of antibiotic course as temperature.
- **Renal function** tests will be measured **before** patients received colistin or tigecycline and **after 72 hours from first dose**:

- Serum creatinine level (scr).
- **Hepatic function** tests will be measured **before** patients received colistin or tigecycline and **after 72 hours from first dose**:
  - Alanine transaminase (ALT)
  - Aspartate transaminase (AST)
  - Serum total bilirubin (TBIL)
- **14 days Survival rate after starting colistin or tigecycline will be recorded.**
- The severity of the illness will be assessed by using the Acute Physiology and Chronic Health Evaluation II (APACHE II) scoring system will be calculated.(Wu et al., 2022).

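### The renal replacement exclusion runs on through the admission, so as written it can remove patients after sealed-envelope allocation; the wording of entry by drug received should be aligned too

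*Protocol*

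**What the plan says.** All references are to the Protocol, section III unless stated.

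- **Study design**: a prospective randomised controlled study. "The method of randomization was a sealed envelope technique".
- **Exclusion criteria**: one bullet reads "Patients received renal replacement therapy before or during admission". The bullet above it ties creatinine clearance to baseline; this one has no such anchor.
- **Inclusion criteria**: adults aged 18 to 70 in intensive care "who received intravenous colistin or tigecycline as antimicrobial drug for treatment their MDR gram negative infection".
- **Study population**: each group is described by the drug taken ("66 patients received intravenous" colistin or tigecycline).
- **Study procedure**: serum creatinine is measured before treatment and 72 hours after the first dose. For survival, "14 days Survival rate after starting colistin or tigecycline will be recorded".
- **Introduction (section I)**: older reports link colistin with "neuromuscular blockade, hematotoxicity and nephrotoxicity and mortality risk", among other effects. The same section says that newer studies find its side effects less common.

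Nothing in the Protocol says that the criteria are checked only before allocation, or that a randomised patient who later meets an exclusion stays in the comparison.

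**The concern.** Randomisation protects a comparison only if who is in the trial is settled before the arm is known. The renal replacement clause covers the whole admission. Follow-up runs to 72 hours for creatinine and to 14 days for survival, so renal replacement in the same admission can readily begin after the envelope is opened. Staff who apply the clause as printed would then drop that patient.

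The event that triggers removal may itself be caused by the allocated drug. The worst renal outcomes could therefore leave the analysis meant to detect them, and could do so more often in one arm. Such patients may also be at higher risk of death, so the survival comparison is exposed as well.

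The wording of entry and groups by drug received raises a related but weaker issue. Read literally, a patient who is randomised but never dosed was never eligible.

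**Working it through.** **1. Can the clause act after allocation?** Allocation is by sealed envelope, and the two drugs are the arms, so dosing follows allocation. Creatinine is followed to 72 hours after the first dose and survival to 14 days after the start of treatment. The exclusion window covers the admission and has no end at allocation. So the clause can act after allocation.

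**2. Reproduce the plan's own figure.** Inputs from Sample size calculation: two-sided Fisher's exact test, p1 = 0.58, p2 = 0.261, alpha 0.05, power 0.95, ratio 1:1. Power is the sum, over all pairs (x, y) with Fisher p ≤ 0.05, of Bin(x; 66, 0.58) × Bin(y; 66, 0.261). The result is 0.9501125. With both proportions at 0.261 the rejection probability is 0.0316077. Both match the Protocol. With both at 0.58 it is 0.0318.

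**3. Illustrate selective removal.** The Protocol gives no rate, so these counts are assumptions: k = 1, 3 or 6 patients, all with the event. As shares of an arm they are 1/66 = 1.5%, 3/66 = 4.5% and 6/66 = 9.1%. Both arms have the same true proportion p. Draw x and y from Bin(66, p). Removal from one arm tests (x − k)/(66 − k) against y/66; removal from both tests (x − k)/(66 − k) against (y − k)/(66 − k). As a reference, the same enumeration with Bin(66 − k, p) against Bin(66, p) removes k patients from one arm without selection.

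False-positive rate (0.032 at k = 0):

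| p | k | One arm, events only | Both arms, events only | One arm, no selection |
|---|---|---|---|---|
| 0.261 | 1 | 0.043 | 0.035 | 0.039 |
| 0.261 | 3 | 0.076 | 0.045 | 0.040 |
| 0.261 | 6 | 0.168 | 0.066 | 0.041 |
| 0.58 | 1 | 0.040 | 0.034 | 0.039 |
| 0.58 | 3 | 0.046 | 0.042 | 0.039 |
| 0.58 | 6 | 0.074 | 0.042 | 0.044 |

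The last column shows that most of the rise at k = 1 comes from the discreteness of Fisher's test: unequal arms of 65 and 66 already give 0.039. The figures of 0.076, 0.168 and 0.074 are mainly due to selection.

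**4. Shift in the estimate.** With no true difference, the apparent difference is p − (66p − k)/(66 − k). For k = 3:

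- p = 0.261: 0.261 − (17.226 − 3)/63 = 0.035
- p = 0.58: 0.58 − (38.28 − 3)/63 = 0.020

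At the planned proportions the difference is 0.58 − 0.261 = 0.319. Removing three event patients gives:

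- from the p1 arm: (38.28 − 3)/63 − 0.261 = 0.299
- from the p2 arm: 0.58 − (17.226 − 3)/63 = 0.354

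**5. Power is not the main issue.** If 10% of one arm and 5% of the other are lost without selection, 59 and 63 remain, and power is 0.945. The concern is bias.

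**The case against.** **Loose past tense.** The Protocol uses the past tense for planned acts: the randomisation method, the groups and the data analysis. Study procedure has "patients received colistin or tigecycline and" in a line that schedules tests before the first dose as well as after it, so there the verb plainly means a future act. This largely disposes of the literal reading of the inclusion criterion. Whether randomised but undosed patients are analysed is an analysis-set question that a statistical analysis plan, not shown here, may settle. A death before the first dose also gives no drug-related reason for unequal loss between arms. A reader might infer that the Protocol deliberately makes dosing a gate to entry; it does not support that. Only a wording correction stands.

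**The renal clause may mean history up to screening.** It is listed as an exclusion, beside a baseline criterion, and nothing calls it a withdrawal rule. A reader might infer that the Protocol orders removal after allocation; it does not say so. But tense does not explain an explicit window that runs through the admission, and the baseline anchor in the bullet above shows that a time limit could have been written. The ambiguity stands. On renal safety, the planned measure is creatinine at 72 hours, so the effect there concerns mainly renal replacement started by then.

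**Other criteria.** A reader might extend the point to "Patient is on any other nephrotoxic drug". That bullet is in the present tense with no window past allocation and reads naturally as status at entry.

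**Size.** The 0.168 needs all six removed patients to be events from one arm, about 35% of the 17.2 expected there (6/17.226). Nothing in the Protocol supports that count. With equal removal at 0.58 the rate stays below 0.05 throughout. Nor do the documents show that colistin would lose more patients: the Introduction also says that newer studies find its side effects less common, and it reports a mortality risk for tigecycline as well.

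**Conclusion.** The point holds for the renal replacement exclusion. As written, it can remove a randomised patient because of an event after allocation that may follow from treatment, and so can bias the renal-safety and 14-day survival comparisons. For the wording of entry and groups by drug received, it holds only as a matter of alignment with the randomised design.

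The size is illustrative. It rests on assumed counts of 1 to 6 removed patients, all with the event, and on 0.58 and 0.261 used only as event levels, since the Protocol does not name their endpoint. Under those assumptions the false-positive rate lies between 0.040 and 0.168 for one-arm removal and between 0.034 and 0.066 for equal removal. One removal, or three at 0.58, stays below the nominal 0.05. A reader might infer that the trial's type I error is already inflated, or will reach 0.168. The documents support neither; they show an open route to bias of unknown size. It should be closed because eligibility timing belongs in the Protocol, and a later analysis plan cannot recover follow-up that was never collected.

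**What to change.** - State that all eligibility criteria and consent are settled before the envelope is opened.
- Reconcile the renal replacement exclusion with entry decided before allocation, so that an event after allocation does not remove a randomised patient from the comparison. No clinical rule on renal replacement is proposed.
- In Inclusion criteria and Study population, replace the wording by drug received with wording that patients are eligible for, and then allocated by randomisation to, colistin or tigecycline.
- In Study procedure, add that 14-day vital status is recorded for every randomised patient, including any never dosed. Counting survival from the first dose is not an error in itself.

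The cost is wording in four sections, plus continued follow-up of the few patients affected. The 66 + 66 sample size, alpha and planned power are unchanged.

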### **Exclusion criteria:**

- Patient admitted to intensive care unit younger than 18 years or older than 70 years (14).
- Liver transplantation patients.
- Patients are chronic kidney disease (CKD on hemodialysis or baseline creatinine clearance (crcl) < 10 ml/min (estimated by Cockcroft Gault equation).
- Patients received renal replacement therapy before or during admission.
- Patient is on any other nephrotoxic drug (vancomycin, aminoglycosides, NSAIDs, cyclosporine, amphotericin B, etc.) (Aggarwal & Dewan, 2018).
- Pregnant and lactating women (16).
- Patients refused the consent of the study.

### **Study procedure:**

- Demographic and medical history for all patients included in this study will be recorded.
- Complete physical examination for all patients included in this study will be taken.
- Basic routine investigation for all patients included in this study will be measured as Complete blood Count test (CBC), blood pressure and temperature.
- Improvement of signs and symptoms after the end of antibiotic course as temperature.
- **Renal function** tests will be measured **before** patients received colistin or tigecycline and **after 72 hours from first dose**:

- Serum creatinine level (scr).
- **Hepatic function** tests will be measured **before** patients received colistin or tigecycline and **after 72 hours from first dose**:
  - Alanine transaminase (ALT)
  - Aspartate transaminase (AST)
  - Serum total bilirubin (TBIL)
- **14 days Survival rate after starting colistin or tigecycline will be recorded.**
- The severity of the illness will be assessed by using the Acute Physiology and Chronic Health Evaluation II (APACHE II) scoring system will be calculated.(Wu et al., 2022).

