### **Statistical analysis:**

All statistical analysis will be performed by using SPSS version 23. The demographic and clinical characteristics of patients will be expressed as mean  $\pm$  standard deviation (SD). Student's t-tests or Mann-Whitney tests will be used to compare between groups. Chi-square tests or exact tests (Fisher's exact test or likelihood ratio test) will be used to detect the existence of association between variables.

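### The renal safety comparison is not tied to each patient's own baseline creatinine, so comparing 72-hour levels, as the wording allows, would lose much of the power to detect kidney injury

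*Protocol*

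**What the plan says.** - **Objective.** Protocol, Aim and objectives: the trial is to "compare the clinical outcomes and safety between colistin and tigecycline for multi-drug resistant gram negative bacteria". Safety is therefore part of the aim, and the Introduction lists nephrotoxicity among the side effects reported for colistin.
- **Measure.** Protocol, Study procedure: the renal item is "Serum creatinine level (scr"). Renal function "tests will be measured before patients received colistin or tigecycline and after 72 hours from first dose". No change score, ratio, fold-rise or staging is named. Hepatic tests (ALT, AST, total bilirubin) follow the same two-time schedule.
- **Entry.** Protocol, Exclusion criteria: the renal limits are haemodialysis or renal replacement therapy and "baseline creatinine clearance (crcl) < 10 ml/min (estimated by Cockcroft Gault equation"). Clearance from 10 ml/min upward is otherwise eligible.
- **Analysis.** Protocol, Statistical analysis: "Student's t-tests or Mann-Whitney tests will be used to compare between groups". For categorical data, "Chi-square tests or exact tests (Fisher's exact test or likelihood ratio test) will be used to detect the existence of association between variables". Neither sentence mentions creatinine, and no baseline adjustment is stated.

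**The concern.** Drug nephrotoxicity typically shows as a marked rise in a minority of patients. A patient's creatinine at 72 hours is the starting value multiplied by whatever happened since. If arms are compared on the 72-hour value alone, the starting values enter as noise. A doubling from 0.6 to 1.2 mg/dL would look unremarkable, while a stable 3 mg/dL would look abnormal.

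Randomisation keeps such a comparison free of systematic bias, so the problem is precision. In a trial of 66 per arm, a real excess of kidney injury on one drug could easily give a non-significant difference in levels, although the baseline value that would have revealed it was collected.

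**Working it through.** **1. The plan's own figure.** Protocol, Sample size calculation: two-sided Fisher's exact test, proportions 0.58 and 0.261, alpha 0.05, power 0.95. Exact enumeration at 66 per arm gives power 0.9501125 and actual alpha 0.0316077, as stated; 65 per arm gives 0.9491. The calculation is right, but no endpoint is named for the two proportions. It therefore supplies neither a renal event rate nor a creatinine SD, and what follows uses assumed values.

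**2. How far eligible baselines can differ.** Cockcroft-Gault for a man: creatinine = (140 − age) × weight / (72 × clearance). For an assumed 50-year-old of 70 kg the numerator is 90 × 70 = 6300.
- clearance 10: 6300 / 720 = 8.75 mg/dL
- clearance 30: 6300 / 2160 = 2.92
- clearance 60: 6300 / 4320 = 1.46
- clearance 120: 6300 / 8640 = 0.73

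Eligible baselines can thus differ 12-fold (8.75 / 0.73), against an assumed injury effect of 1.5- to 2.5-fold.

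**3. Hand calculation on the log scale.** Assume injury in 25% v 5%, rises uniform between 1.5- and 2.5-fold, within-patient noise of 12%, and log baseline SD s.
- Log rise in an injured patient: mean 0.68, variance 0.022.
- Difference between arms in mean log creatinine: 0.20 × 0.6825 = 0.1365.
- Variance of the log-ratio, 25% arm: 0.25 × 0.022 + 0.25 × 0.75 × 0.6825² + 0.12² = 0.107. In the 5% arm: 0.05 × 0.022 + 0.05 × 0.95 × 0.6825² + 0.12² = 0.038. Sum 0.145.
- Log-ratio to baseline: SE = √(0.145 / 66) = 0.047; 0.1365 / 0.047 = 2.9; power ≈ Φ(2.9 − 1.96) ≈ 0.83.
- Log 72-hour level: each arm gains s². With s = 0.5, SE = √((0.145 + 0.50) / 66) = 0.099, z = 1.38, power ≈ 0.28. With s = 0.3, SE = √((0.145 + 0.18) / 66) = 0.070, z = 1.95, power ≈ 0.49.

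**4. Simulation** under the same assumptions (median baseline 1.1 mg/dL, 66 per arm, at least 2000 trials per scenario; ranges cover repeated runs):

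| Comparison | Power, 25% v 5% |
|---|---|
| 72-hour level, t-test | 0.31–0.34 (log-SD 0.5); 0.56–0.58 (log-SD 0.3) |
| 72-hour level, Mann-Whitney | 0.23–0.26 (log-SD 0.5); 0.39 (log-SD 0.3) |
| Ratio to baseline, Mann-Whitney | 0.52–0.53 |
| Log-ratio t-test, or log level adjusted for log baseline | 0.82–0.85 |
| Proportion with ≥1.5-fold rise, Fisher | 0.84–0.87 |

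**5. Sensitivity to case mix.** Baselines were generated from Cockcroft-Gault, with injury in 40% v 10% and every injury classified correctly. Power for 72-hour levels (t-test / Mann-Whitney):
- all clearances 60–120: 0.82 / 0.72
- 20% of patients at 10–60: 0.31 / 0.52
- uniform 10–120: 0.29 / 0.36
- log-uniform 10–120: 0.36 / 0.27

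The injury proportion gives 0.97–0.98 throughout, and a t-test on change from baseline gives 0.81–0.94.

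**6. Sensitivity to the size of the rise.** With rises of 1.2- to 2.0-fold and 25% v 5%, the 1.5-fold cut-off falls to 0.59, against 0.71 for the baseline-adjusted analysis.

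**The case against.** The strongest reply is that the Protocol nowhere says 72-hour levels will be compared. It collects a pre-treatment value, which naturally serves a change or ratio. Its t-test sentence is generic and fits change scores equally well, and it lists tests suited to an injury proportion. How baseline enters the model, and laboratory cut-offs, are often left to a statistical analysis plan. That stands in part: the loss follows from a reading the wording allows, not one it commits to. What remains is that the only stated test for continuous data is unadjusted, and that nothing links the comparison to the baseline.

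A second reply is that the missing injury threshold is not the cause. That is correct. A log-scale analysis using baseline reaches 0.82–0.85 with no threshold, so most of the gap comes from ignoring baseline. A simulation in which every true rise is at least 1.5-fold also favours a 1.5-fold cut-off; step 6 shows the cut-off losing when rises are smaller.

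Third, the size depends on an unseen case mix. If every patient had clearance of 60 ml/min or more, the loss would be much smaller (0.82 / 0.72 against 0.98 for 40% v 10%).

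**Conclusion.** The point holds as a gap in the stated analysis that is cheap to close. Followed literally, the plan can compare 72-hour creatinine between arms and waste the baseline. At 66 per arm and injury in 25% v 5%, that means power of roughly 0.24–0.58 instead of 0.82–0.87. The figures rest on the assumed injury rates, fold-rise, 12% within-patient noise and baseline spread. The direction does not depend on them as long as baseline creatinine varies appreciably between patients.

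A reader might infer more than the documents support:
- **That raw levels are the planned analysis.** The text permits this but does not state it.
- **That the lack of a kidney-injury definition is what costs the power.** Step 4 shows otherwise. A definition is worth adding because it gives clinicians a risk to weigh.
- **That a non-significant result would be declared equal renal safety.** The Protocol makes no such claim.
- **That the liver tests suffer the same loss.** They share the two-time structure, so the same adjustment is sensible, but no calculation was made for them and no size is claimed.
- **That the renal entry limit is wrong.** It matters here only as a source of spread.

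**What to change.** In Protocol, Statistical analysis, state:
1. Arms are compared on log 72-hour creatinine adjusted for log pre-treatment creatinine in a linear model, and reported as a ratio of geometric means with 95% CI. A t-test on the log-ratio to baseline is a near-equivalent alternative. Naming the log-scale analysis matters, because a Mann-Whitney test on the ratio recovers only part of the power (0.52–0.53).
2. The proportion of patients whose 72-hour creatinine is at least 1.5 times their own pre-treatment value is also reported by arm, with risk difference, 95% CI and Fisher's exact test.
3. ALT, AST and bilirubin are analysed with the same baseline adjustment.

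The cost is wording only. Both values are already scheduled, and no visit, test, eligibility rule or treatment changes. The one downside is that the cut-off discards information when rises are modest (0.59 v 0.71), which is why the continuous analysis should accompany it.

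### 14-day survival is timed from the first dose of either drug, so it is undefined for a randomised patient who starts neither, and time zero falls after allocation

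*Protocol*

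**What the plan says.** - **Study design** calls the trial a "Prospective randomized controlled study" and adds: "The method of randomization was a sealed envelope technique". It does not say when the envelope is opened relative to the first dose. The protocol describes no blinding.
- **Study procedure** sets the survival outcome: "14 days Survival rate after starting colistin or tigecycline will be recorded". The renal and hepatic tests are timed "after 72 hours from first dose".
- **Study population** describes each group in the form "66 patients received intravenous" followed by the drug, not as patients assigned to it.
- **Inclusion criteria** admits patients "who received intravenous colistin or tigecycline as antimicrobial drug for treatment their MDR gram negative infection", so receipt of a study drug is part of eligibility.

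No section uses randomisation as the origin for any outcome. None says what is recorded for a patient who is randomised but not treated.

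**The concern.** Randomisation makes the two groups comparable at the moment of allocation. Here the survival clock starts later, at an event that need not happen and whose timing could depend on which envelope was opened. With no blinding described, the arm is known from then on. A patient who dies, withdraws or is moved to other treatment before any study drug is given has no day 0. The receipt-based wording of the groups and of eligibility then gives a reason to leave that patient out altogether.

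Two things are at stake. First, a patient who starts neither drug has no defined survival outcome, and if staff follow the protocol literally, day-14 status may never be collected. No later analysis decision can recover data that were not recorded. Second, if the delay to first dose or the decision to start differs between arms, the patients who reach time zero are selected differently in each. Survival is the outcome least open to judgement in this protocol, so it is worth protecting.

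**Working it through.** **1. The plan's own figure.** Sample size calculation gives 66 per group (132 in total) for a two-sided Fisher's exact test with p1 = 0.58, p2 = 0.261, alpha 0.05 and power 0.95. Full enumeration of the exact test at 66 + 66 gives:

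- power 0.950112 (stated 0.9501125);
- actual alpha, evaluated at 0.261, of 0.031608 (stated 0.0316077);
- power 0.9491 at 65 per group, just short of the target.

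The sample size reproduces and is not in question. The protocol does not say which outcome p1 and p2 describe.

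**2. Who has a day 0 under the wording of Study procedure.**

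| Randomised patient | Day 0 defined? |
|---|---|
| Starts the assigned drug | Yes, at first dose |
| Starts the other drug | Yes, at first dose of that drug |
| Starts neither drug | No |

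The gap is therefore confined to patients who start neither drug. For the other two rows the outcome exists, but its origin falls after allocation.

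**3. Size of a one-sided loss (illustration).** Assumptions, none of them given in the protocol: true 14-day survival *s* is the same in both randomised arms; a fraction *d* of one arm dies before any dose; nobody in the other arm does. Survival among starters in the affected arm is s / (1 − d). I use s = 0.58, borrowing the value of p1 only as a convenient number.

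| d | Survival among starters | Spurious difference | Fisher rejection rate |
|---|---|---|---|
| 0% | 58.0% | 0 | 3.2% |
| 2% | 0.58/0.98 = 59.2% | 1.2 points | 4.1% |
| 5% | 0.58/0.95 = 61.1% | 3.1 points | 5.2% |
| 10% | 0.58/0.90 = 64.4% | 6.4 points | 10.3% |

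The rejection rates use 65, 63 and 59 starters in the affected arm against 66. With s = 0.42 the differences are 0.9, 2.2 and 4.7 points, and the rejection rates 4.0%, 4.5% and 8.0%.

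In counts, assuming 40% mortality in both arms: 0.40 × 66 = 26.4 deaths. If 3 of them in one arm have no clock, observed mortality is (26.4 − 3)/63 = 37.1%. If 6, it is (26.4 − 6)/60 = 34.0%. The other arm stays at 40%.

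**4. Equal losses.** If the same fraction dies before dosing in both arms, each arm shows s / (1 − d) and the difference is zero. With 3 such deaths in each arm, mortality is 37.1% in both.

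**5. Power if non-starters in both arms have no outcome.** With 2%, 5%, 10% or 15% missing from each arm, 65, 63, 59 or 56 remain per arm. Power at the planned proportions is 94.9%, 94.8%, 92.5% or 90.6%. This applies to survival only if p1 and p2 refer to it.

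**The case against.** The strongest reply is that this may have no practical effect. Both drugs begin with an intravenous loading dose in intensive care. If the envelope is opened just before that dose, the two origins almost coincide and hardly anyone is lost. A drug not yet given cannot cause a death, so deaths before dosing should be balanced by randomisation unless delays or starting decisions differ by arm, and nothing in the protocol shows that they do. Even under one-sided loss, the rejection rate at 2% or 5% stays close to or below the nominal 5%. Survival is not named as primary. All of this stands, and it limits the size of the point.

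Three stronger readings are tempting, and the text does not support them:

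- *Anyone not started on the assigned drug has no outcome.* The sentence names either drug, so a patient who starts the other one has a day 0.
- *The trial does not compare the randomised groups.* That follows only if some patients never start, or start at delays that differ by arm. The protocol does not say that either happens.
- *The lack of a stated analysis population is itself an error.* That may be set in a statistical analysis plan that is not at hand.

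What the reply does not remove is the rule itself. The protocol fixes the time origin and words both groups and eligibility by receipt. That is stated text, not a detail left for later.

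**Conclusion.** The point holds in a limited form. As worded, the survival outcome is undefined for any randomised patient who starts neither drug, and its time zero follows allocation. The receipt-based wording in Study population and Inclusion criteria reinforces this and sits badly with a randomised design.

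The bias cannot be sized from the protocol. It is near zero if dosing follows randomisation at once or if losses are balanced. It is about 1 to 6 points if 2% to 10% of one arm only die before dosing, and matters for the error rate mainly at the upper end of that range. Those loss rates, their one-sidedness and the survival levels used are all assumptions. This is a minor point, worth acting on because the correction is nearly free.

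**What to change.** 1. **Study procedure:** record vital status at day 14 after randomisation for every randomised patient, and compare survival by assigned group whether or not that drug was started.
2. **Study population and Inclusion criteria:** describe the groups as patients *randomised to* each drug, and eligible patients as those *requiring treatment with* one of the study drugs, instead of by receipt. Changing the survival sentence alone would leave wording that still drops non-starters.
3. **Study design:** state when the envelope is opened relative to the first dose.
4. Keep the first-dose clock only for the 72-hour renal and hepatic tests.

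The cost is a few sentences and one recorded date, which is known when the envelope is opened. Non-starters need a day-14 vital status check. No laboratory test is added, and the sample size stays at 132.
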